#### **Statistical Methods**

Baseline demographic disease characteristics, including medical history and exposure to study drug, will be summarized by treatment group using descriptive statistics. Continuous variables will be summarized with mean, median, standard deviation, minimum, and maximum. For categorical or ordinal data, frequencies and percentages will be displayed for each category.

The primary efficacy variables will be analyzed using multiple imputation approach with mixed-effect model for repeated measure (MMRM) based on the FAS with adjustment for missing data due to lack of efficacy or adverse events assuming the WOMAC scores would on average return to baseline values. The imputed data for patients discontinued from the study treatment due to lack of efficacy or AEs will be centered at the mean baseline value. The missing data for patients who discontinued treatment due to other reasons will be imputed under missing-at-random assumption. Sensitivity analysis using tipping point approach with multiple imputation will be performed to assess the robustness of the results due to data that may be missing not-at-random.

For analysis of continuous secondary endpoints, the analysis method will be the same as that used for the primary variables. For analysis of categorical variables in secondary endpoints, eg, proportions of patients with  $\geq 30\%$  improvement in the WOMAC pain subscale scores at week 24, the Cochran Mantel Haenszel approach stratified by the randomization strata will be used with missing data considered as non-response.

Safety data including treatment-emergent adverse events and treatment-emergent adverse events of special interest, vital signs, physical examinations, laboratory tests, electrocardiograms, and anti-drug antibody formation will be listed and summarized by treatment group.

---

**LIST OF ABBREVIATIONS AND DEFINITIONS OF TERMS**

5-ASA	5-aminosalicylic acid
AA	Adjudicated arthropathy
ACE	Angiotensin-converting enzyme
ADA	Anti-drug antibody
AE	Adverse event
AESI	Adverse event of special interest
ALT	Alanine aminotransferase
ARB	Angiotensin receptor blocker
AST	Aspartate aminotransferase
AUC	Area under the curve
bpm	Beats per minute
C max	Maximal concentration
CRF	Case report form (electronic or paper)
CRO	Contract research organization
C trough	Trough concentrations
CTCAE	Common Terminology Criteria for Adverse Events
DA	Destructive arthropathy
DMC	Data Monitoring Committee
EC	Ethics Committee
ECG	Electrocardiogram
eCRF	Electronic case report form
EDC	Electronic data capture
EOS	End of study
EOT	End of treatment
EQ-5D-5L	EuroQoL 5 Dimensions 5 Level Questionnaire
ESR	Erythrocyte sedimentation rate
FAS	Full analysis set
FDA	Food and Drug Administration
FSH	Follicle-stimulating hormone
GCP	Good Clinical Practice
GFR	Glomerular filtration rate
HbA1c	Hemoglobin A1c
HCRU	Healthcare Resource Utilization
hs-CRP	High-sensitivity C-reactive Protein
ICF	Informed consent form
ICH	International Council for Harmonisation
IRB	Institutional Review Board

---

IV	Intravenous
IWRS	Interactive web response system
JR	Joint replacement
K-L	Kellgren-Lawrence
mAb	Monoclonal antibody
MedDRA	Medical Dictionary for Regulatory Activities
MMRM	Mixed-effect Model for Repeated Measures
MRI	Magnetic Resonance Imaging
NGF	Nerve growth factor
NRS	Numeric Rating Scale
NSAID	Non-steroidal anti-inflammatory drug
OA	Osteoarthritis
PGA	Patient Global Assessment
PK	Pharmacokinetic
PPS	Per protocol set
Pre-op	Pre-operative
PT	Preferred term
QRS	Complex of Q, R, and S waves on an electrocardiogram
Q4W	Every 4 weeks
Q8W	Every 8 weeks
RBC	Red blood cell
Regeneron	Regeneron Pharmaceuticals, Inc.
SAE	Serious adverse event
SAF	Safety analysis set
SAP	Statistical analysis plan
SAS	Statistical Analysis Software
SC	Subcutaneous
SD	Standard deviation
SF-36	36-item Short Form Medical Outcomes Study Questionnaire Version 2
SOC	System organ class
SUSAR	Suspected unexpected serious adverse reaction
TBL	Total bilirubin
TEAE	Treatment-emergent adverse event
TrkA	Tyrosine kinase type 1
TSQM	Treatment Satisfaction Questionnaire for Medication
ULN	Upper limit of normal
US	United States
WBC	White blood cell

WOCBP	Woman of child-bearing potential
WOMAC	Western Ontario and McMaster Universities Osteoarthritis Index
WPAI-OA	Work Productivity and Activity Impairment-Osteoarthritis

## 1. INTRODUCTION

Chronic musculoskeletal pain affects a large portion of the global population. A significant cause of chronic musculoskeletal pain is due to osteoarthritis (OA). Osteoarthritis is a progressive, chronic disease caused by the breakdown and loss of cartilage of the joints, which leads to pain in the hips, knees, hands, feet, and spine. It is characterized by focal areas of loss of articular cartilage in synovial joints accompanied by subchondral bone changes, osteophyte formation at the joint margins, thickening of the joint capsule and mild synovitis. Symptoms and disability increase with increasing age. The prevalence of OA in patients aged 65 and older is 60% in men and 70% in women, and continually rising (Sarzi-Puttini 2005).

Non-steroidal anti-inflammatory drugs (NSAIDs) are the mainstay of treatment in patients with mild-to-moderate OA. The efficacy of NSAIDs is well-documented, albeit modest, but their use is associated with a number of risks (Bingham 2007) (Bjordal 2004) (Makarowski 2002) (Silverstein 2000). The risks associated with long-term therapy with NSAIDs, in particular, have been well-characterized and include gastrointestinal (GI) bleeding and increased risk of cardiovascular events (Lanas 2011) (Trelle 2011). Non-steroidal anti-inflammatory drugs have limited efficacy in many OA patients; those with advanced OA typically try several NSAIDs and must often move to other therapies such as opioids.

Treatment guidelines for OA suggest that opioids may be used in OA only if management with NSAIDs is ineffective, intolerable, or otherwise contraindicated (American College of Rheumatology Subcommittee on Osteoarthritis Guidelines 2000). However, the use of opioids is limited by central nervous system effects, nausea and vomiting, constipation, and potential for abuse and dependence. In addition, opioid use may be associated with both acute and chronic side effects, including drowsiness, dizziness, gastrointestinal intolerance, motor imbalance, respiratory depression, and even death. Opioid use must be closely monitored in patients who are vulnerable or are potentially vulnerable to abuse or addiction. Moreover, there is no evidence to support superiority of opioids over other available pain medications. While the efficacy of opioids in treating pain over a short duration is supported by research data (Smith 2016), long-term efficacy has not been evaluated.

Thus, there remains an unmet medical need for alternative treatment options to opioids that have a more effective analgesic effect, particularly since there are a significant number of patients who are intolerant to or do not get adequate pain relief from the currently available treatment options. Inadequate pain relief has a profound impact on the quality of life for millions of people worldwide with an associated substantial cost to society, including healthcare cost (Salmon 2016) and loss of productivity (Dibonaventura 2011).

Neurotrophins are a family of peptide growth factors that play a role in the development, differentiation, survival and death of neuronal and non-neuronal cells (Chao 2006). Nerve growth factor (NGF) was the first neurotrophin to be identified, and its role in the development and survival of both peripheral and central neurons during the development of the nervous system is well characterized (Crowley 1994) (Smeyne 1994). In the adult, NGF is not required as a survival factor but acts as a pain mediator that sensitizes neurons (Pezet 2006). Nerve growth factor activity is mediated through 2 different membrane-bound receptors, the high-affinity tyrosine kinase type 1 (TrkA) and the low-affinity p75 neurotrophin receptors.

By acting upstream of several relevant molecular pathways, the NGF/TrkA system appears to play a major role in the control of pain. Administration of NGF has been shown to provoke pain in both rodents (Lewin 1994) and humans (McArthur 2000), while NGF antagonists have been shown to prevent hyperalgesia and allodynia in animal models of neuropathic and chronic inflammatory pain (Ramer 1999). Humans with mutations in TrkA (hereditary sensory and autonomic neuropathy IV) or NGF (hereditary sensory and autonomic neuropathy V) have been identified with a loss of deep pain perception (Einarsdottir 2004) (Indo 1996). In addition, NGF is known to be elevated in the synovial fluid of patients with rheumatoid arthritis and other types of arthritis (Aloe 1992) (Halliday 1998), and to be up-regulated in injured and inflamed tissues in conditions such as cystitis, prostatitis, and chronic headache (Lowe 1997) (Miller 2002) (Sarchielli 2001).

Fasinumab (also known as REGN475) is a fully-human high-affinity monoclonal antibody directed against NGF. By selectively blocking NGF, fasinumab has the potential to be effective in modulating NGF-associated pain without some of the adverse side effects of other analgesic medications, such as opioids and NSAIDs. Following an evaluation of the safety and tolerability of the antibody in a single-ascending-dose first-in-human study (study R475-PN-0817), a proof-of-concept study evaluating the effect of fasinumab on pain in 217 patients with OA of the knee was completed (study R475-PN-0901, see current edition of Fasinumab Investigator's Brochure). Three intravenous (IV) doses of fasinumab were evaluated (0.03, 0.1, 0.3 mg/kg every 8 weeks [Q8W]). All three doses, compared with placebo, were associated with statistically significant improvement in pain as evaluated by walking knee pain, the Western Ontario and McMaster Universities Osteoarthritis Index (WOMAC), and the Patient's Global Impression of Change questionnaire. Additionally, the R475-PN-1227 study in patients with OA revealed significant efficacy in the WOMAC pain subscale score for each of the doses of fasinumab evaluated (1 mg, 3 mg, 6 mg, and 9 mg given every 4 weeks [Q4W]) compared with placebo (see current edition of the Investigator's Brochure). Results from recent clinical studies with other anti-NGF antibodies, tanezumab (Pfizer) and fulranumab (Janssen), also support the role of NGF in pain modulation in patients with pain due to OA of the knee and hip (Brown 2012) (Hefti 2006) (Lane 2010) and in patients with chronic low back pain (Katz 2011) (Kivitz 2013).

In all clinical studies completed to date, fasinumab was generally well tolerated. Arthralgia, joint swelling, peripheral edema, hypoesthesia, and myalgia were more frequently reported in fasinumab-treated patients than in placebo-treated patients. In neurological evaluations, abnormalities in vibration sense were more frequent in the fasinumab patients than in the placebo patients. These adverse events (AEs) or physical examination abnormalities associated with fasinumab were generally mild to moderate in intensity and were transient (see current version of the Investigator's Brochure).

Data from studies of tanezumab and fulranumab demonstrated these molecules were associated with an increased risk of destructive arthropathy (DA), a unique clinical form of rapidly progressive arthropathy over and above that seen in the normal progression of osteoarthritis. Analyses of the tanezumab data by its sponsor, defined by anatomic pathological criteria on specimens obtained on joint replacement (JR), revealed that the risk of DA increases with tanezumab dose and is further increased with the concomitant use of chronic NSAIDs (>90 days) (Lane 2010). Most cases of DA occurred in joints with a documented history of OA.

Based on the potential risk of DA identified in tanezumab and fulranumab, the United States (US) Food and Drug Administration (FDA) placed this class of anti-NGF antibodies on clinical hold in 2010. Following a review of anti-NGF antibody clinical data in March 2012, the FDA determined that clinical studies of anti-NGF therapies could resume if mitigation strategies are implemented to minimize the risk of DA. To address concerns about potential events of DA, a risk-mitigation approach is also being implemented for all fasinumab studies, as outlined in Section 9.6.1.1. This approach includes sensitive, prospective, and rigorous radiologic screening for select changes in joint structure. The patients who develop these changes, which are referred to throughout this document as adjudicated arthropathy (AA), are required to discontinue study therapy.

Since the removal of the FDA clinical hold, Regeneron has conducted or initiated several clinical trials of fasinumab. In all clinical studies to date, fasinumab was associated with a low rate of discontinuations due to adverse events. Patients treated with fasinumab generally had more frequent events than did placebo-treated patients of arthralgia, joint swelling, peripheral edema, altered peripheral sensation (eg, paresthesia, dysesthesia), and myalgia.

In 2012, studies of other anti-NGF monoclonal antibodies (mAbs) identified adverse changes in the sympathetic nervous system of mature animals of several species (rat and non-human primate). These effects include a reversible decrease in neuron volume. To date, no statistically significant or consistent effects of fasinumab on the sympathetic nervous system have been detected in animal studies with up to 6-months of treatment. Nonetheless, based on the potential risk of sympathetic nervous system toxicity associated with these other anti-NGF mAbs in animal studies, a risk mitigation approach is being implemented for all fasinumab studies, as outlined in Section 9.6.1.2.

In the phase 2/3 study of fasinumab in patients with pain due to OA of the knee or hip (R475-PN-1227), 26 AA events occurred in 24 patients. There was an increase in AA events that appeared to be related to greater fasinumab dose. Although these events were milder than the severe DA events presented at the 2012 FDA Arthritis Advisory Committee, in consideration of the lack of an observed dose response for efficacy in OA, the benefit-risk ratio was deemed unfavorable for the fasinumab 6 mg Q4W and 9 mg Q4W doses in patients with OA, in comparison to the other fasinumab doses that were studied, (ie, 1 mg Q4W and 3 mg Q4W). The dose regimens that were being evaluated in the phase 3 studies for OA pain in the knee or hip included 1 mg Q8W, 1 mg Q4W, 3 mg Q4W, and 6 mg Q8W. In April 2018, the independent Data Monitoring Committee (DMC) recommended discontinuing 6 mg Q8W and 3 mg Q4W (expected to have similar exposure to 6 mg Q8W) based on a review of unblinded data in an on-going study in the fasinumab phase 3 OA program (R475-PN-1523). Subsequently a small Regeneron team reviewed the data and agreed with this recommendation. The DMC noted imbalances in clinically relevant adverse events including time to total joint replacement, peripheral edema, arthralgia and a trend towards early fractures. The phase 3 program for OA pain in the hip or knee will continue to evaluate fasinumab 1 mg with the highest dose regimen of 1 mg Q4W, which is supported by the independent DMC as having a favorable benefit-risk profile.

Fasinumab is currently being evaluated in 2 phase 3 studies in patients with pain due to OA. Study R475-PN-1523 is currently ongoing and is designed to assess the long-term safety and efficacy of multiple doses of fasinumab compared to placebo in patients with OA of the hip or knee. Study R475-OA-1611 is designed to compare the efficacy and safety of fasinumab to placebo and to naproxen, a standard-of-care NSAID for moderate-to-severe pain due to OA of the hip or knee. The phase 3 study described here, R475-OA-1688, is designed to compare the efficacy and safety

of fasinumab to placebo, and to a pooled NSAID arm (celecoxib or diclofenac, which are additional standard-of-care NSAIDs for moderate-to-severe pain due to OA of the hip or knee).

Additional background information on fasinumab and the development program can be found in the current edition of the Investigator's Brochure.

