### **2.2. Secondary Objective(s)**

The secondary objectives of the study are:

- To evaluate the efficacy of fasinumab compared to NSAIDs, when administered for up to 24 weeks in patients with pain due to OA of the knee or hip
- To assess the safety and tolerability of fasinumab compared to placebo and compared to NSAIDs, when administered for up to 24 weeks in patients with pain due to OA of the knee or hip
- To characterize the concentrations of fasinumab over time when administered for up to 24 weeks in patients with pain due to OA of the knee or hip
- To evaluate the immunogenicity of fasinumab administered for up to 24 weeks in patients with pain due to OA of the knee or hip

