###### Analysis

All AEs reported in this study will be coded using the currently available version of the Medical Dictionary for Regulatory Activities (MedDRA®). Coding will be to lowest level terms. The verbatim text, the preferred term (PT), and the primary system organ class (SOC) will be listed. The focus of AE reporting in the clinical study report will be on TEAEs. Post-treatment AEs and all AEs during the study will be summarized similarly as TEAEs.

Summaries of all TEAEs by treatment group will include:

- The number (n) and percentage (%) of patients with at least 1 TEAE by SOC and PT
- TEAEs by severity (according to the grading scale outlined in Section 9.5.1), presented by SOC and PT
- TEAEs by relationship to treatment (related, not related), presented by SOC and PT
- Treatment-emergent AESIs (defined with a PT or a pre-specified grouping)

Deaths and other SAEs will be listed and summarized by treatment group.

Treatment-emergent adverse events leading to permanent treatment discontinuation will be listed and summarized by treatment group.

In addition, AESIs will be reported according to the adjudicated diagnosis. Imaging data related to AA including change from baseline in joint space width will be summarized.

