#### 4.6.2. Adverse Events of Special Interest

Adverse events of special interest (AESI) are AEs (serious or non-serious) required to be monitored, documented, and managed in a pre-specified manner as described in the protocol. In this study, the AESI are listed below (as provided in the protocol):

- Adjudicated Arthropathy (as confirmed by adjudication) selected using an eCRF specific tick box on the AE page.
- Sympathetic nervous system dysfunction (as diagnosed after consultation with an appropriate specialist, such as a neurologist and/or a cardiologist) selected using an eCRF specific tick box on the AE page.
- Peripheral sensory AEs that require a neurology or other specialty consultation selected using an eCRF specific tick box on the AE page.
- Joint replacement surgery (defined as elective joint replacement surgery not due to new or worsening AE) using eCRF specific tick box on the AE page.

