### **5.8.1. Adverse Events**

The verbatim text, the preferred term (PT), and the primary system organ class (SOC) will be displayed in subject listings. Summaries that include frequencies and proportions of patients reporting AEs will include the PTs and the SOCs.

For details on handling missing data and partial dates, see Section 6.3.

Summaries of AE incidence by treatment group will include:

- Overview of TEAEs, summarizing number of events, summarizing number and percentage of patients within the specified category
  - Total number of TEAEs
  - Total number of serious TEAEs
  - Total number of AESIs
  - Total number of serious AESIs
  - Patients with any TEAEs
  - Patients with any serious TEAEs

- Patients with any AESI's
- Patients with any serious AESIs
- Patients with any TEAEs leading to permanent study treatment discontinuation
- Patients with any TEAEs leading to withdrawal from study
- Patients with any TEAEs leading to death
- TEAEs by SOC and PT
  - All TEAEs
  - TEAEs by severity: mild, moderate or severe
  - TEAEs resulting in permanent study treatment discontinuation
- Study drug-related TEAEs by SOC and PT
  - All TEAEs
  - TEAEs by severity: mild, moderate or severe
  - TEAEs resulting in permanent study treatment discontinuation
- TEAEs by PT
  - All TEAEs
  - TEAEs resulting in permanent study treatment discontinuation
- Post-treatment AEs by SOC and PT
  - All post-treatment AEs
  - Post-treatment AEs by severity: mild, moderate or severe
- Serious TEAEs by SOC and PT
  - All serious TEAEs
- Post-treatment Serious AEs by SOC and PT
- All serious AEs on study by SOC and PT
- Non - Serious TEAEs by SOC and PT
  - All non-serious TEAEs
- Post-treatment Non-Serious AEs by SOC and PT
- All non-serious AEs on study by SOC and PT
- All AEs on study by SOC and PT
  - All AEs
  - All AEs by severity: mild, moderate or severe
- Deaths

Counts will be provided according to treatment group for each PT within each SOC. Percentages will be calculated using the number of patients in each treatment group using the respective SAF.

Primary SOCs will be sorted by descending frequency of the 'Fasimumab 1 mg SC Q4W' treatment group. Within each primary SOC, PTs will be sorted by decreasing frequency of investigational product.

A second type of table with counts of each primary SOC in decreasing order of frequency will be provided. A third type of table with counts of each PT in decreasing order of frequency will also be provided.

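### For fasinumab 1 mg, fractures (other than subchondral insufficiency fractures), peripheral edema and arthralgia get only SOC/PT counts by arm; no grouped fracture term or between-arm interval is pre-specified

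*Protocol*

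**What the plan says.** **The signals.** Protocol section 1 reports that in April 2018 the DMC, reviewing unblinded data from another study (R475-PN-1523), recommended stopping two regimens: "The DMC noted imbalances in clinically relevant adverse events including time to total joint replacement, peripheral edema, arthralgia and a trend towards early fractures". The Amendment 3 Global entry in the Amendment History places the fracture trend in the 6 mg Q8W group. The same Introduction says of earlier fasinumab studies: "Patients treated with fasinumab generally had more frequent events than did placebo-treated patients of arthralgia, joint swelling, peripheral edema, altered peripheral sensation". The 1 mg Q4W regimen continued, and the DMC regarded its benefit-risk profile as favorable.

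**The objective.** Protocol section 2.2 lists: "To assess the safety and tolerability of fasinumab compared to placebo and compared to NSAIDs".

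**The analysis.** The AESIs (Protocol 9.4.3; SAP 4.6.2 and 5.8.2) are adjudicated arthropathy (AA), joint replacement, sympathetic dysfunction, and peripheral sensory events needing specialist consultation. Fracture, peripheral edema and arthralgia are not among them. Protocol 10.4.4.1 provides for term groupings in one place only: "Treatment-emergent AESIs (defined with a PT or a pre-specified grouping". All other events follow SAP 5.8.1: "Counts will be provided according to treatment group for each PT within each SOC". That section adds tables of SOC totals and of PTs by frequency, and repeats the layout for post-treatment AEs and for all AEs on study.

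**The concern.** The natural safety question for the surviving dose is whether the harms seen at the stopped doses also occur at 1 mg, and how large any excess is against placebo and against NSAIDs. For three of the four harms the DMC named, the plan gives percentages per arm but no estimate of the difference and no statement of its uncertainty.

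Fractures carry a second problem. If they are coded under several PTs, each row holds few patients. The SOC total is no substitute, because it is not specific to fracture. An excess could then be spread so thinly that no single row stands out. A grouping chosen after unblinding could still be produced, but it would be open to the charge of selection, which SAP section 1 sets out to avoid by pre-specifying the analyses.

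**Working it through.** **Figure to reproduce.** None. The documents give no rate, sample size or power for fractures, edema or arthralgia. The arm sizes used below do agree with the plan's own efficacy powers. With 20% dropout, 480 vs 480 and a difference of 0.51 (SD 2.3) give 93.0% (stated: about 92%), and 480 vs 240 with 1.1 (SD 2.4) give over 99% (stated: at least 99%).

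**Inputs.** Planned randomized numbers (Protocol 6.1; SAP 2.2): fasinumab 1 mg 600, placebo 300, pooled NSAIDs 300 + 300 = 600. *Assumptions:* fracture risk 3% on fasinumab and 1% on comparator; at most one fracture per patient; two-sided Fisher p≤0.05 as a yardstick for visibility only, since the plan tests no AE.

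**Step 1, grouped.** Expected patients: 600×0.03 = 18; 300×0.01 = 3; 600×0.01 = 6. The Newcombe interval is built from Wilson limits (l, u) for each arm:

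lower = d − √[(p₁−l₁)² + (u₂−p₂)²]; upper = d + √[(u₁−p₁)² + (p₂−l₂)²]

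The Wilson limits are 1.91% to 4.69% for 18/600, 0.34% to 2.90% for 3/300, and 0.46% to 2.16% for 6/600.

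- Against placebo: 2.0 − √(1.09² + 1.90²) = −0.2; 2.0 + √(1.69² + 0.66²) = 3.8 points. Fisher p for 18/600 vs 3/300 is 0.064.
- Against NSAIDs: 2.0 − √(1.09² + 1.16²) = 0.4; 2.0 + √(1.69² + 0.54²) = 3.8 points.

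Exact Fisher power, summing binomial probabilities over all tables with p≤0.05, is 45% against placebo and 65% against NSAIDs.

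**Step 2, other assumed rates (grouped).**

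| Comparator vs fasinumab | Power vs placebo | Power vs NSAIDs |
|---|---|---|
| 0.5% vs 1.5% | 17% | 31% |
| 1% vs 2% | 15% | 22% |
| 2% vs 4% | 30% | 48% |
| 1% vs 3% | 45% | 65% |
| 1% vs 4% | 74% | 91% |

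**Step 3, the 3% vs 1% case split over PTs.** The chance that at least one row reaches p≤0.05 is 1 − Π(1 − power of row k), treating rows as independent.

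- Six equal terms: about 3 fasinumab patients per row against 0.5 (placebo) or 1 (NSAIDs). Power per row is 0.33% and 3.5%. Any row: 1 − 0.9967⁶ = 2% and 1 − 0.965⁶ = 19%.
- Ten equal terms: power per row is 0.07% and 0.58%. Any row: 1 − 0.9993¹⁰ = 0.7% and 1 − 0.9942¹⁰ = 6%.
- Eight unequal terms (40%, 20%, the rest equal): the 40% row alone has power 10.2% and 22.6%. Any row: 1 − 0.898×0.993×0.998 = 11% and 1 − 0.774×0.941×0.994 = 28%.

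In every split tried, row-by-row detection is below the grouped figure. The size of the loss is not fixed: against NSAIDs it runs from 65% down to 28% in one case and down to 6% in another.

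**Step 4, edema and arthralgia.** The documents do not suggest that these split over many terms, so Step 3 is not applied to them. Their gap is only the missing difference and interval.

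**The case against.** **No comparison at all?** A reader might infer that fasinumab is not compared with placebo or NSAIDs for these harms. That goes too far. SAP 3.4 puts all three arms in the safety set, and SAP 5.8.1 tabulates them side by side. What is absent is an estimated contrast with its uncertainty.

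**No dedicated fracture or joint analysis?** This is also too strong. Subchondral insufficiency fractures are a component of AA (Protocol 9.6.1.1). AA is summarized overall and by subtype, with Kaplan-Meier and a Cox hazard ratio with 95% CI against placebo (SAP 5.8.7). Worsening joint pain is summarized from a questionnaire (SAP 4.6.8). These analyses narrow the gap without closing it: AA covers one fracture type, the questionnaire covers knees, hips and shoulders, and the Cox comparison is with placebo only.

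**Altered peripheral sensation?** One might add it to the list, because the AESI covers events needing a consultation. But Protocol 9.6.1.3 requires referral and AESI reporting for any event lasting 2 months, and neurological findings are summarized separately (SAP 5.8.6). It is not part of this point.

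**Is the fracture signal weak?** It was a trend, in 6 mg Q8W, in another study, and the DMC supported 1 mg. That stands. It is a reason to keep the analysis descriptive.

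**Are the figures assumed?** Yes: the rates, the number of terms and their split. An even split flatters the argument. A simple Wald interval against placebo would also mislead, because it just excludes zero where Newcombe does not. A reader can also add up fracture rows by hand, but without an agreed term list two readers may reach different totals.

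**Conclusion.** The point holds in a limited form. Fractures other than subchondral insufficiency fractures, peripheral edema and arthralgia are reported for 1 mg Q4W only as per-arm counts and percentages by SOC and PT. No grouped fracture term is pre-specified, and no risk difference or ratio with a 95% CI against placebo or pooled NSAIDs is planned for any of the three, despite the secondary objective. That much follows from the documents without any assumption.

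The dilution argument applies to fractures only and rests on assumed rates and coding. At 3% vs 1%, grouping makes the imbalance visible in about 45% (placebo) and 65% (NSAIDs) of trials, and less often when read row by row, by an amount that cannot be fixed in advance. Even grouped, 18/600 vs 3/300 gives −0.2 to 3.8 points, which includes zero. Grouping gives a clearer estimate but does not make this an adequately powered fracture study. A reader might infer that the plan hides a known harm at 1 mg; the documents report no such harm at that dose and support no such reading. This is an inexpensive reporting improvement that should be made before unblinding.

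**What to change.** In SAP 5.8.1, before unblinding, fix a term list for any fracture, and groupings for peripheral edema and for arthralgia/joint swelling. For each, over first dose to Week 44, report n (%) per arm and the risk difference with a 95% Newcombe CI for fasinumab 1 mg minus placebo and for fasinumab 1 mg minus pooled NSAIDs. Add a Kaplan-Meier curve of time to first fracture. Label all of it descriptive, outside the multiplicity procedure, with no alpha.

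The tools are already in the SAP: standardized MedDRA queries in 5.10.3.1, and descriptive contrasts with intervals in 5.8.7. The cost is the term lists and a few tables and figures, with no new data, visits or patients. The small downside is a few more descriptive intervals, one of which may exclude zero by chance and must be read as such.
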